## Study Protocol and Analysis

[figure not shown]
### *Experimental Design*

Subjects participated in a total of seven visits: Screening, Drug Dispensation x 2, Compliance x 2, and Laboratory Session x 2 (described below). Upon completion of both the first randomized double blind drug cycle and a drug washout, subjects crossed over to complete the second drug cycle.

To increase subject retention, and given previous work that even a single dose of tolcapone can influence decision making (Kayser et al., 2012), we evaluated a 5-day treatment period. This 5-day dosing regimen included a weekend, thereby both allowing us to capture self-reported weekend drinking (Friday-Sunday) on study drug, and also permitting subjects to return on the final day of the treatment window for the Laboratory Session (on either a Monday or a Tuesday evening). Based on previous work with this subject population, we felt that subjects might display higher drinking over the weekends and therefore that we would be best able to capture a drug effect during this time.

The trial was registered at ClinicalTrials.gov, NCT 02740582.

Figure 1

### *Subjects*

Non-treatment seeking individuals with AUD (ages 21 – 40; Table 1) were recruited via a Craigslist posting, which requested that subjects be “moderate to heavy alcohol drinkers”, as well as referrals from study subjects. The age range was chosen to minimize safety concerns regarding possible tolcapone effects on hepatic function (Tan, Eastment, Poudel, & Hubbard, 2015) and to avoid age-related changes in the dopamine system that can begin as early as age 40 (Volkow et al., 1996). While there are important differences in treatment seeking and non-treatment seeking subjects (Rohn et al., 2017), we intentionally chose to evaluate the effects of tolcapone in a non-treatment seeking population to minimize both regression to the mean and the need to assess subject motivation. Using this population also represents an intrinsically more conservative approach, in that subjects who are not motivated to reduce alcohol consumption may be less likely to show large declines in alcohol consumption.

Following a brief telephone screening procedure, potentially eligible subjects were invited in for a screening visit.

### *Screening Visit*

Written informed consent was obtained in accordance with the Institutional Review Board at the University of California, San Francisco. Study visits took place in the research clinic within the

Li Ka Shing building at UC Berkeley. Acute intoxication was assessed via a breath alcohol sensor (Alcomate, Palisades Park, NJ); subjects were required to have a 0.00 blood alcohol concentration (BAC) to provide consent. To capture multiple dimensions of alcohol use, inclusion criteria incorporated both self-reported alcohol consumption (>10 drinks/week for females and >14 drinks/week for males) and a requirement to meet DSM-5 criteria for AUD in the last 12-months (as assessed via the AUD section of the Mini-International Neuropsychiatric Interview (Sheehan et al., 1998)). The mean AUDIT score in the study population was 14.3, and 98.1% of subjects showed an AUD severity of moderate or severe (Table 2).

Female subjects were administered a pregnancy test, and were required to be non-pregnant, non-lactating, and using a reliable contraceptive method. Exclusion criteria included a positive urine drug screen (with the exception of THC), or use of any illicit substance within 72 hours of the start of the study; current attempts to either reduce or eliminate alcohol consumption (e.g. via current enrollment in an alcohol or drug treatment program); history of alcohol related complications (e.g., liver failure/cirrhosis, pancreatitis, esophageal varices); abnormal results on tests of liver injury (alanine aminotransferase (ALT) or aspartate aminotransferase (AST) values greater than the upper limit of normal); regular use of any drugs with catecholaminergic actions such as SSRIs or amphetamines; and severely low or uncontrolled high blood pressure. Information about subjects' past substance use, psychiatric history, medical history, current medications, and family history of problem drinking was collected. The study clinician performed a physical examination, a 12-lead electrocardiogram, and a blood draw to evaluate markers of liver injury. To establish a baseline prior to laboratory bar sessions, subjects were also asked to perform components of a standard field sobriety test that assessed horizontal gaze nystagmus, walk-and-turn, and a timed one-leg stand. Together with evaluation of BAC, these direct measures of neurological function were used to ensure that subjects were free of alcohol-induced motor impairments prior to dismissal from the laboratory bar sessions. The screening visit concluded with the administration of behavioral inventories including the Alcohol Use Disorders Identification Test (AUDIT; (Saunders, Aasland, Babor, de la Fuente, & Grant, 1993)) and the Barratt Impulsiveness Scale (BIS; (Patton, Stanford, & Barratt, 1995)). Eligible subjects were scheduled into groups of 4-8 subjects for study drug administration.

### *Study Drug*

Study drug was provided by Valeant Pharmaceuticals. Wellspring Compounding Pharmacy (Berkeley, CA) held the study blind and re-compounded study drugs to add 10 mg riboflavin to both tolcapone and placebo in order to facilitate medication compliance checks: ultraviolet light was used to detect the presence of riboflavin in the urine at the Check Visit and the Laboratory Session. Enrolled subjects self-administered tolcapone (100 mg) or placebo three times a day (TID) for 5 days, for a total of 300 mg tolcapone per day. This dosing regimen is in keeping with the FDA approved dosing regimen for Parkinson's disease, the approved indication for tolcapone treatment.

### *Drug Administration Visit*

Subjects returned to the clinic on a Thursday or Friday morning to begin the study drug administration cycle. Given that the half-life of tolcapone is 2.5 hours, we expect the drug reached steady-state at approximately 12.5 hours (5 half-lives). The initiation of drug administration on a Thursday or Friday was designed to capture weekend drinking (see below)

during the 5-day administration window. Subjects completed a side effects scale, a pulse and blood pressure check, and a pregnancy test (females). Subjects ingested their first dose of study drug under clinical supervision and were instructed to continue medication administration three times daily, ending on the 5th day (Monday or Tuesday) when they ingested their final dose at the start of the Laboratory Session (Figure 1). Subjects and investigators were blind to the medication condition. Medication bottles were equipped with Medication Event Monitoring System (MEMS) caps (AARDEX, Zurich, Switzerland) that generated a time stamp each time the bottle was opened. MEMS caps data were downloaded at each study visit.

#### *Weekend Drinking*

Subjects were instructed on “standard alcoholic drink” volumes and provided an information card for reporting weekend drinking. Subjects were contacted via a HIPAA compliant text message system each day during medication administration to capture the number of alcoholic drinks the subject had consumed the previous night. To confirm standard drink values, the type, amount, and volume of alcohol were reviewed in person with the study staff at the Compliance Check. “Weekend drinking” was calculated as the total number of alcoholic drinks from Friday to Sunday.

#### *Compliance Check*

Subjects returned to the clinic for a compliance check the day prior to their laboratory session. This visit assessed medication compliance (including evaluation of MEMS cap data), collected side effects information, and obtained a urine sample to confirm riboflavin fluorescence. All subjects had positive riboflavin screens at their study visits. MEMS caps data indicated that on at least 4 of the 5 treatment days, 95.5% of the subjects opened their MEMS cap 1x/day or more, 90.0% opened the MEMS cap 2x/day or more, and 59.1% opened the MEMS cap 3x/day or more, demonstrating reasonable medication compliance.

#### *Laboratory Session*

Subjects arrived at the clinic for the laboratory session (in groups of 4-8 subjects) on a Monday evening (for subjects started on a Thursday) or Tuesday evening (Friday start). Subjects were asked to fast for 1 hour prior to the start of the session and were drug screened and assessed for acute intoxication upon arrival. Those subjects with a positive screen or BAC were not permitted to consume alcohol. Subjects ingested the final dose of study medication immediately prior to completing the tasks below.

#### *Delay Discounting Task*

Detailed methods have been previously described and validated in a similar subject population (Boettiger et al., 2007; Mitchell et al., 2005). At the start of each trial, subjects were cued to one of four trial types: “Want”, “Don’t Want”, “Sooner”, and “Larger”. For each of these trial types, subjects were presented with two hypothetical alternatives on the left and right sides of the screen: a smaller amount of money available sooner and a larger amount available at a future point in time. Subjects made a button press to select the option associated with the left and right sides of the screen in accordance with trial type. Subjects selected the option they wanted in the “Want” trials and the option they did not want in the “Don’t Want” trials. “Sooner” and “Larger” trials, in which subjects simply identified the sooner and larger options respectively, were included as control conditions to ensure that subjects followed task instructions. The choice was

presented as one of six variations: a “sooner” option of “today” versus a “later” option of five future time points (1 week, 2 weeks, 1 month, 3 months, or 6 months), or a “sooner” option of “3 months” versus a “later” option of “6 months”. The “larger” value consisted of six amounts (\$1, \$2, \$5, \$10, \$20, or \$100), while the “sooner” value represented one of four percentages (70%, 85%, 90%, and 95%) of the larger delayed amount. Subjects completed 6 blocks of 47 trials each (for a total of 282 trials) presented in pseudorandom order and were permitted to take breaks between each block. The “Want” condition comprised 50% of all trials, the “Don’t Want” condition comprised 34%, and the two control conditions combined comprised 16% of the trials. The primary behavioral outcome was the impulsive choice ratio (ICR), which represents the ratio of the number of sooner choices to the number of total choices in the “Want” condition. More impulsive subjects are thus characterized by higher ICR values. Previous work has demonstrated that this intuitive score correlates strongly with other model-based measures of delay discounting (Kayser et al., 2012; Kayser, Mitchell, Weinstein, & Frank, 2015; Mitchell et al., 2005). Study participants completed this task together in the same testing room prior to the laboratory bar.

#### *Assessment of Side Effects*

Subjects completed a side effects scale reporting the extent to which they were experiencing 17 side effects (scored on a 0 – 3 scale, indicating “none”, “slight”, “moderate”, and “severe” effects) at each study visit. Because tolcapone may be hepatotoxic, the side effects were selected, in consultation with the FDA, to monitor effects associated with compromised liver function. All subjects who reported a side effect as “moderate” or “severe” were immediately evaluated by the study clinician. Over the course of the study, 11 subjects reported a moderate or severe side effect; 4 of those subjects were taking tolcapone at the time (see Results).

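### The 4-of-11 side-effect count cannot be read as tolcapone versus placebo, and may understate tolcapone's share

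*Combined protocol and SAP*

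**What the plan says.** Experimental Design gives the schedule: "Subjects participated in a total of seven visits: Screening, Drug Dispensation x 2, Compliance x 2, and Laboratory Session x 2". Assessment of Side Effects says that a 17-item scale was completed "at each study visit", with items chosen to pick up impaired liver function because tolcapone may be hepatotoxic. The result covers the whole trial: "Over the course of the study, 11 subjects reported a moderate or severe side effect". It is divided by what the subject was taking when the report was made: "11 subjects reported a moderate or severe side effect; 4 of those subjects were taking tolcapone at the time". The sentence then refers to Results, which are not part of the document.

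The visit descriptions place the scale relative to dosing:

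- **Drug Administration Visit:** the scale is listed first, and only afterwards does the text say "Subjects ingested their first dose of study drug under clinical supervision".
- **Compliance Check:** this visit, the day before the Laboratory Session, "collected side effects information".
- **Laboratory Session:** the final dose of the cycle is taken here.
- **Crossover:** the washout is 3 or 10 days.

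**The concern.** The rule behind the count separates tolcapone from everything else, and everything else is more than placebo. It also takes in visits at which the subject was on neither drug. A reader who sees 4 of 11 will naturally subtract and compare 4 with 7, although the two numbers come from different amounts of observation.

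The rule also interacts with sequence. A symptom that appears or persists after the tolcapone cycle falls on the non-tolcapone side if tolcapone came first, and has no visit at which to be recorded if tolcapone came second. This matters because the items were chosen to watch for liver effects, and the only liver blood test in the visit descriptions is at screening. The tolerability statement thus depends on how these reports are attributed. The efficacy outcomes are not affected.

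**Working it through.** **1. The plan's own figure.** 4/11 = 36.4%, leaving 11 − 4 = 7 subjects whose condition is not stated. These are observed counts without visit-level data, so they cannot be re-derived. What can be checked is what they cover.

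**2. Visits by condition**, for a subject who completes both cycles:

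| Visit | State when the scale is completed |
|---|---|
| Screening | Before any drug |
| Dispensation 1 | Before any drug (scale described ahead of first dose) |
| Compliance 1, Laboratory 1 | On cycle 1 drug |
| Dispensation 2 | Off drug, after cycle 1 |
| Compliance 2, Laboratory 2 | On cycle 2 drug |

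This gives 2 tolcapone visits, 2 placebo visits and 7 − 4 = 3 off-drug visits. Screening is uncertain: the side-effects section says every visit, but the Screening Visit section does not list the scale. Without it there are 2 off-drug visits. The non-tolcapone side therefore covers 5 visits (or 4) against 2 for tolcapone.

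**3. Scales completed after the tolcapone cycle, by sequence.**

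- Tolcapone first: three (Dispensation 2, off drug; Compliance 2 and Laboratory 2, on placebo). A late effect reported at any of them counts as not on tolcapone.
- Tolcapone second: none, because the second Laboratory Session is the last listed visit.

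**4. Sensitivity of the share.** Two separate what-if calculations, not to be added together. Each assumes one condition per subject.

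(a) Suppose k of the 7 reported at off-drug visits. Restricted to on-treatment reports, tolcapone's share is 4/(11 − k):

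| k | Tolcapone : placebo | Share |
|---|---|---|
| 0 | 4 : 7 | 36.4% |
| 1 | 4 : 6 | 40.0% |
| 2 | 4 : 5 | 44.4% |
| 3 | 4 : 4 | 50.0% |
| 4 | 4 : 3 | 57.1% |
| 7 | 4 : 0 | 100% |

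(b) Suppose instead that j of the 7 were after-effects of tolcapone. The share is (4 + j)/11: 36.4% at j = 0, 45.5% at j = 1, 54.5% at j = 2, and 100% at the bound j = 7.

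Neither k nor j is in the documents. Both mechanisms can only raise the share, but zero is allowed for each.

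**5. Washout.** At a half-life of 2.5 hours, the stated minimum of 24 half-lives is 24 × 2.5 = 60 hours, about Monday evening to Thursday morning. A full 3 days is 72/2.5 = 28.8 half-lives. The plan's figure reproduces, and residual drug in cycle 2 is negligible. Any late effect would have to be one that outlasts the drug.

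**The case against.** The strongest reply is that the document makes no comparison. It does not say that 7 subjects were on placebo, gives no denominator by condition and draws no conclusion. The sentence follows a description of clinician evaluation and points to Results, where the breakdown may be given. Safety is not among the outcomes or tests in Statistical Analysis. All of this is correct, and it limits the point to how the sentence can be read.

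A reader might go further and infer that 4 of 11 does understate tolcapone's share and does put after-effects on the wrong side. The documents do not support that. It requires at least one of the 7 to have reported off drug or to have had an after-effect, and neither is shown. If all 7 were on placebo with no after-effects, 36.4% is right.

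A reader might also set 4 against the number expected from tolcapone's share of visits. That benchmark assumes equal reporting at every visit and treats 11 subjects as 11 independent reports, although one subject may report at several visits and under both drugs. It should not be used.

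The washout argument stands for residual drug. It does not show that a liver effect, or its symptoms, would have resolved; equally, the documents do not show that any persisted. That the scale came before the dose at dispensation is inferred from the order of the text.

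**Conclusion.** The concern holds in a limited form. The count cannot serve as a tolcapone-versus-placebo comparison, because the non-tolcapone side covers 4 or 5 visits against 2 and the condition of the other 7 subjects is not given. The tolcapone-to-placebo split could lie anywhere from 4:7 to 4:0 if each subject belongs to one condition, so 36.4% may understate tolcapone's share. Whether it does cannot be settled from the documents. The difference in follow-up between sequences comes from the listed schedule and does not depend on unseen data: late effects are recorded as not on tolcapone in one sequence and not recorded in the other.

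This rests on the scale preceding the first dose at dispensation visits, on the listed visits being complete, and, for the higher visit count, on the scale being used at screening. It is worth correcting because the correction is cheap; it does not show a tolerability problem with tolcapone.

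**What to change.** Tabulate subjects with moderate or severe reports by visit, sequence and condition. Use four conditions: tolcapone, placebo, before any drug, and off drug after cycle 1, with the last shown separately by the preceding drug and not merged into either arm. Give the number of subjects exposed under each condition, and state a rule for subjects who report under more than one.

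Base any head-to-head comparison on the Compliance and Laboratory visits of each cycle, so that both drugs are observed over the same two visits. State that subjects who took tolcapone second have no post-treatment assessment.

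The document reads as that of a completed trial, so for this trial the gap can probably only be declared as a limitation. If data are still being collected, the same scale could be sent once after cycle 2 through the existing text-message system.

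The cost is a little more tabulation of data already held, plus one message per subject if the optional step is possible. The tolerability statement may become less favourable to tolcapone.

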#### *Laboratory alcohol consumption*

The laboratory session included a proof-of-principle, group laboratory bar protocol. All behavioral testing occurred prior to any alcohol consumption. This protocol was designed to create a more naturalistic setting for social drinkers. Laboratory sessions took place in a room outfitted with couches, coffee tables, and music to achieve a social bar-like atmosphere. Minimal guidance on social interaction was prescribed: subjects were seated together, instructed not to use phones during the experiment, and encouraged to interact during the laboratory session. To best account for variability in administration times across subjects, the final dose of study medication was ingested in the laboratory, and the laboratory session was timed to be in the peak effective window of this dose. Eighty-minutes following the final medication administration, subjects were given a priming drink. Alcohol content in the priming drink was calculated based on the subject’s weight and sex and designed to bring the blood alcohol concentration (BAC) to approximately .04. The formula for calculating grams of pure alcohol was based on the Widmark formula (Posey & Mozayani, 2007):  $g = kg * r * BAC * 10$ , where  $r = .68$  for males and  $.55$  for females, and where  $BAC = .04$ . Subjects were required to consume the priming drink within 15 minutes. Both alcohol and soda were refrigerated and drinks were served without ice to maintain a 1:3 ratio.

Following the priming drink, BAC was assessed via a breath alcohol sensor (Alcomate, Palisades Park, NJ). Subjects received 4 (empty) cups to represent the maximum of 4 drinks they could order during the 1-hour session. Each drink was ½ the size of each subjects’ initial priming drink and valued at \$4. Subjects were told that they had a pre-paid tab valued at \$16 and the value of

any drinks they did not consume would be added to their study payment. Salty snacks and water were available throughout the session.

After the 1 hour drinking session, subjects were provided with dinner. Subjects were required to have  $BAC \leq 0.04$  and to pass a Field Sobriety Test (see above) before they were eligible for dismissal. All participants were driven home via car service (either Lyft or Uber).

#### *Crossover*

After the laboratory session and following a washout window, subjects were crossed over to the alternate study drug. Given the 2.5-hour half-life of tolcapone (Jorga, 1998), a minimum of 3 days of washout ensured that, if tolcapone were administered during the first cycle, at least 24 half-lives had passed before the second cycle began. To control for day-of-the-week effects on behavior, the crossover cycle was scheduled to begin on the same day as the first cycle, resulting in either a 3-day or 10-day washout window based on scheduling availability. To control for social dynamics, lab bar group composition was maintained across medication cycle crossover whenever possible; however not all subjects completed the laboratory sessions (see Statistical Analysis below).

#### *Genetic Analysis*

Although our sample size was not powered to examine genotype, an exploratory analysis was conducted to ascertain whether the previously published relationship between COMT and decision-making might also be apparent in this study sample. DNA was extracted from saliva samples by the UCSF Genomics Core using Gentra Puregene reagents and protocols and quantified using the Pico Green method (Molecular Probes/Invitrogen). COMT genotyping was carried out by direct DNA sequencing of genomic DNA using fluorescent Sanger chemistry and analyzed using Mutation Surveyor from SoftGenetics LLC. Sequencing genotype accuracy was cross-validated with TaqMan (Applied Biosystems, Foster City, CA).

#### *Statistical Analysis*

Our sample size was calculated based on previous changes in alcohol consumption observed in a laboratory bar setting (Mitchell, Bergren, Chen, Rowbotham, & Fields, 2009). We calculated that, for a mean difference of .5 drinks per session and a standard deviation of 1.2 drinks, we would need a sample size of at least 48 subjects to achieve an alpha of .05 with a power of .80 for the pilot group laboratory bar protocol. Due to low enrollment and high drop-out rates in this subject population, we projected that we would need to enroll 80 subjects to achieve a final sample size of 48 subjects.

We enrolled a total of 62 enrolled subjects, and 55 subjects successfully completed the weekend drinking paradigm. Of the 7 subjects who did not complete the paradigm, 1 was excluded for non-adherence to the study protocol, 1 asked to withdraw, 1 experienced a drug dispensing error, 1 did not show for the scheduled visit, and 3 subjects had positive urine drug screens at the first lab bar visit and ended their participation. 50 of 55 subjects completed both lab bar sessions. The 5 who did not complete both lab bar sessions had positive urine drug screens and were excluded from drinking at these sessions. Three additional subjects were excluded from the DDT decision making task analysis for performing at less than 60% accuracy on control trials designed to assess task compliance (Mitchell et al., 2005), leaving 47 subjects for the DDT analysis.

The primary outcome measure of “weekend drinking” was defined as total number of alcoholic drinks consumed (Friday to Sunday) to capture drinking on study drug across dosing schedules. Secondary outcome measures included the change in impulsive choice ratio (ICR) on the DDT task following tolcapone, the number of alcoholic drinks consumed in the lab bar, and the impact of genotype on tolcapone effects. Data is reported as mean  $\pm$  SEM unless otherwise noted.

Change in weekend drinking and ICR on tolcapone versus placebo were assessed using a within subjects paired t-test. Differences in DDT responses across genotypes were assessed using a one-way ANOVA. The relationship between tolcapone effects on weekend drinking and ICR was assessed with correlation analysis. All statistical tests were conducted using VassarStats and Microsoft Excel V15.23.2.

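### The randomised two-cycle crossover is analysed without a period or order term, so a shift between cycles would cost the primary test power and could create a false correlation between the two drug effects

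*Combined protocol and SAP*

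**What the plan says.** Experimental Design describes a two-period crossover in randomised order: "Upon completion of both the first randomized double blind drug cycle and a drug washout, subjects crossed over to complete the second drug cycle".

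Statistical Analysis gives one method for both the primary outcome and the impulsive choice ratio (ICR): "Change in weekend drinking and ICR on tolcapone versus placebo were assessed using a within subjects paired t-test". It then adds: "The relationship between tolcapone effects on weekend drinking and ICR was assessed with correlation analysis". The primary analysis has 55 of 62 enrolled subjects and the ICR analysis has 47. No period, cycle, order or sequence term is mentioned in any section, and the text gives neither the allocation ratio nor the number analysed per order.

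The Crossover section does control some things. The starting weekday is matched ("the crossover cycle was scheduled to begin on the same day as the first cycle"), bar groups are kept together where possible, and a washout of 3 or 10 days deals with drug carryover. None of these concerns a first versus a second exposure.

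**The concern.** In a crossover, anything that changes between cycles is added to the drug difference in one order and subtracted from it in the other. Randomising the order makes this tend to cancel in the mean difference. It does not remove it from the variance of the differences, or from the association between two sets of differences.

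A shift is plausible in both outcomes, though not shown. Drinking is self-reported under close monitoring in each cycle: "Subjects were contacted via a HIPAA compliant text message system each day during medication administration". The same long task is repeated at both laboratory sessions: "Subjects completed 6 blocks of 47 trials each (for a total of 282 trials) presented in pseudorandom order".

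Two things are at stake. The primary test may lose power for no benefit. More seriously, the correlation could be read as evidence that the drug lowers drinking by changing impulsivity, when all it reflects is that both measures moved between cycles.

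**Working it through.** **The plan's own figure.** The sizing is "for a mean difference of .5 drinks per session and a standard deviation of 1.2 drinks", giving "at least 48 subjects to achieve an alpha of .05 with a power of .80 for the pilot group laboratory bar protocol". The normal approximation for a paired test is (1.2 × (1.960 + 0.842) / 0.5)² = 45.2, so 46. The exact noncentral-t calculation, two-sided 5%, gives power 0.799 at 47 and 0.807 at 48. The stated 48 reproduces, as a paired test with no period shift. It concerns the lab bar outcome; no SD is given for weekend drinking, so the rest is in SD units.

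**Inputs.** From Statistical Analysis: n = 55 (drinking) and n = 47 (ICR, hence at most 47 for the correlation). Assumed: near-equal orders (28/27 and 24/23); a cycle shift k of 0.25, 0.5 or 0.75 within-order SDs of the paired difference; a drug effect τ = 0.385 SD, which has 80% power at n = 55 when k = 0.

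**Model.** The paired difference is τ + k in one order and τ − k in the other, plus error with SD 1. Ignoring order, the variance of the differences is about 1 + k², so the standard error is inflated by √(1 + k²): 1.03, 1.12 and 1.25. If the orders have n₁ and n₂ subjects, the mean difference is also biased by k(n₁ − n₂)/n.

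**Primary test, approximate check at 28/27, k = 0.5.** Power ≈ Φ(√55 × (0.385 ± b) − 2.005 × √1.25), with b = 0.5 × 1/55 = 0.009. This is Φ(2.923 − 2.242) = 0.75 if the odd subject favours the drug, and Φ(2.788 − 2.242) = 0.71 if not. Simulation agrees:

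| k | Type I error, paired t | Power, paired t (odd subject for / against the drug) | Power with period term |
|---|---|---|---|
| 0.25 | 0.04 | 0.79 / 0.77 | 0.80 |
| 0.5 | 0.03 | 0.75 / 0.71 | 0.80 |
| 0.75 | 0.015 | 0.67 / 0.60 | 0.80 |

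With the lab bar planning ratio instead (0.5/1.2 = 0.417 SD), power at n = 55 is 0.86 with no shift and 0.84, 0.78 and 0.68 for the three shifts (odd subject against the drug). With a period term it stays at 0.86.

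**Imbalance.** Suppose 62 were allocated 31/31 and all 7 losses fell in one order, leaving 31/24. The bias is 7/55 = 12.7% of the shift. At k = 0.5, power is 0.86 or 0.56 depending on direction, against 0.79 with a period term, and type I error stays below 0.05. It exceeds 0.05 only with more imbalance: at k = 0.5, about 0.06 at 32/23 and 0.075 at 33/22.

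**Correlation, n = 47, no true relation.** The expected correlation is r = k₁k₂ / √((1 + k₁²)(1 + k₂²)). For k = 0.5 in both outcomes this is 0.25/1.25 = 0.20.

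| Shift in drinking, ICR | Expected r | False positives, raw | Adjusted for order |
|---|---|---|---|
| 0.25, 0.25 | 0.06 | 7% | 5% |
| 0.25, 0.5 | 0.11 | 11% | 5% |
| 0.5, 0.5 | 0.20 | 28% | 5% |
| 0.75, 0.75 | 0.36 | 75% | 5% |
| 0.5, none | 0.00 | 5% | 5% |

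Shifts of 0.5 in opposite directions give r = −0.20 and the same 28%.

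**The case against.** The shift is entirely assumed. On the scale used here, k = 0.5 and 0.75 are 1.3 and 1.95 times the assumed drug effect on drinking, and the 28% and 75% figures need them in both outcomes at once. At 0.25 SD the damage is slight. The documents also act on one likely source of drift: the Subjects section says non-treatment-seekers were chosen partly to limit regression to the mean, and the Screening Visit section excludes people trying to cut down. ICR is a preference with no right answer, so practice need not move it. Fuller task methods are in cited work that we cannot see, so the absence of a described practice session shows little. With balanced orders the primary test is conservative, not invalid. The correlation is not among the listed outcomes. Counts per order could be in a figure that our text does not reproduce.

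Much of this stands and limits the size of the point: no shift is demonstrated, and the primary test's error rate is safe unless the orders are quite unequal. It does not remove the point. Selecting subjects is not a substitute for a period term. The correlation is a stated analysis whether or not it is a listed outcome, and equal orders do not protect it. A cheap analysis that is correct whatever the shift is better than one that relies on there being none.

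**Conclusion.** The concern holds and should be fixed, although it is not fatal to the trial. For the primary test the issue is efficiency: a loss of about 1 to 3 power points at a 0.25 SD shift, 5 to 9 at 0.5 SD and 13 to 20 at 0.75 SD, with near-equal orders. Material bias needs unequal completion by order, which the available text does not let a reader check. The correlation is the most exposed analysis, because its false-positive rate can rise well above 5% even with balanced orders, provided both outcomes shift. These sizes rest on assumed shifts, normal errors, drug effects that are truly unrelated (for the correlation) and the order splits named above. That a shift adds variance, and that two shifts produce a correlation, follows from the design and needs no assumption about the data.

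**What to change.** Analyse weekend drinking and ICR with period in the model. The simplest form takes cycle 1 minus cycle 2 for each subject, compares the two randomised orders with a two-sample t-test and halves the difference. A mixed model with drug and period fixed and subject random is the alternative. Replace the raw correlation with a partial correlation given order, by subtracting each order group's mean from both difference scores and using n − 3 degrees of freedom. Report numbers per order for the 55 and the 47, and the cycle 1 and cycle 2 means.

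The order is known from the allocation, and the two-sample form runs in the software already named. The text reports final numbers, so in practice this is a re-analysis of collected data and should be labelled as such. It costs one degree of freedom. If there is no shift and the orders are unequal, power falls slightly: from 0.80 to 0.79 at 32/23 and to about 0.78 at 33/22.
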